3.1. Sample Size

Subjects will undergo an initial screen and device demonstration (screening arm) to determine their suitability for an extended trial of the device (extended arm). The target number of subjects for the extended arm is 60 subjects.

Power analysis indicates that in a single tailed test with an alpha level of .05 and a power of .95, the relationship between anticipated effect size and the required sample size is shown in the chart at left. As indicated if we assume an effect size in the range 0.40 – 0.45¹², an appropriate n=60 (ten Study subjects per site).

¹¹ The term “functional visual performance” describes the wearer’s ability to perform various Activities of Daily Living (ADL) with better efficacy and speed than using habitual assistive technology devices. In some cases, because of the hands-free, variable distance, and portable attributes of eSight Eyewear, it is hypothesized that certain ADLs may be possible which were previously impossible or very difficult for certain subjects.

¹² This higher than typical anticipated effect size is an appropriate assumption for this Study design, because of prescriptive inclusion criterion (i.e.: not random population).

About $\frac{1}{3}$ to $\frac{1}{2}$ of subjects who fall into the acuity and visual field inclusion criterion described in Section 3.2 below, demonstrate acute objective improvement and an immediate aptitude with the device. Therefore, we anticipate a total of 150-200 to be enrolled in screening arm of the study, from which 60 will be selected to participate in the extended arm, a three month take-home trial of the device. We expect attrition to be low due to the rigorous screening process for participation.¹³

In addition to a clinician's unit, which incorporates trial lens frames and other unique features for fitting and demonstration, each Site will receive devices for Subjects as they are required. The Site and eSight can, at any time, agree to deploy additional devices to accelerate the collection of data.

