Step 9.01 Re-Assessment of Goals Established in Step 3.01: The Research Assistant or Site Administrator will reassess the Subject's satisfaction with their performance of the personal goals as reported in Step 3.01.

Step 9.02 Re-administration of RAND SF-36 Questionnaire

Tests 9.03 through 9.09 below are repeats of previous tests, intended to assess changes in visual function and functional visual performance over time using eSight Eyewear.

Steps 9.03 through 9.05 are administered by the eyecare physician (Optometrist or Ophthalmologist), or suitably trained and supervised clinical staff.

Step 9.03 Acuity Test – with and without eSight Eyewear (ETDRS or Snellen)

Step 9.04 Mars Contrast Sensitivity Test – with eSight Eyewear

Step 9.05 n/a

Steps 9.06 through 9.09 may be administered by a Research Assistant or a similarly suitable staff person at the clinic (e.g.: CLVT, OT, etc.).

Step 9.06 Minnesota Low Vision Reading Test (MN READ) – with eSight Eyewear

Step 9.07 Cohn-Kanade Facial Recognition Test – with eSight Eyewear

Step 9.08 Melbourne Low-Vision ADL Index Test (MLVAI)

Step 9.09 Final comments, opportunity for freeform feedback, relinquishment of the device.

5. Withdrawal from the Study

A subject may withdraw or be removed from the study at any time without prejudice for any of the following reasons:

- The subject wishes to withdraw
- Occurrence of any serious or adverse device-related effect that is considered by the investigator to represent an unacceptable risk to the subject's physical or mental well-being.
- Occurrence of any physical or mental illness that affects the subject's further participation.
- The subject fails to comply with the requirements of the study.

Time permitting, subjects that withdraw from the study will be replaced by other candidates. Every effort will be made to have withdrawn subjects complete the follow-up procedures (Part 4).

6. eSight Support for Clinical Sites

At each site, before the Study commences, eSight staff will visit the Study location to provide one full day of training with the eSight Eyewear device. This will include the following:

- Training on device demonstration and fitting (trial lenses, adjustment of forehead strap and headband, P.D. adjustment, etc.).
- Explanation of device controls (zoom, video modes, OS/OD displays on/off, saving images).
- Training on various ADLs (bioptic and immersive activities).
- Using direct video feed for television and computer use.

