- **Subject’s Unit:** If the subject is deemed a suitable candidate for an extended evaluation period, they will receive a unit with the user interface customized for them, along with their prescription lenses incorporated, if applicable.
- **Materials for In-Clinic ADL Testing:** Telephone book, kitchen ingredients, etc.

10. Analysis

Some of the data gathered through the course of this study is subjective, and will be used by eSight to prioritize ongoing improvements to the device.

The minimum objective data that will be reported is acuity, contrast, reading speed, without eSight Eyewear at the beginning of the trial, and with eSight Eyewear at its conclusion.

Further objective data is the comparison between the initial VFQ, and RAND SF-36 scores, and the change, if any, in score at the conclusion of the study.

Data analysis will be conducted using IBM SPSS Statistics version 22. The data will be pooled from all testing sites by the Study Manager. Before merging of the data, any systematic differences among testing sites will be assessed. Should such differences exist, they will be considered in subsequent analyses.

Repeated measures Analysis of Variance (ANOVA) and t-tests will be used to compare the effect of the eSight devices on all dependent variables that adhere to the assumptions of parametric data analysis (continuous variables, normal distribution etc.). Categorical variables or those who do not adhere to parametric assumptions will be compared using repeated-measures non-parametric techniques (e.g. Friedman Test). Qualitative data will be analyzed using qualitative description (Sandelowski, 2000).

³⁸ Requires 22” monitor with HDMI input. To be provided by eSight in the event that the study location does not have one available.

The eSight device contains an electronic logging capability, wherein daily on-time hours, and user commands (e.g.: zoom in/out, focus distance, increase/decrease contrast, etc.) are saved to an SD card. No images or video or other information that may personally identify the subject is recorded. These electronic logs may be used to validate user reported usage data³⁹.

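### Section 10 tests all outcomes with no primary comparison or multiplicity rule, and the readable text of Section 3.1 ties its .95 power to no outcome

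*Combined protocol and SAP*

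**What the plan says.** **Power (Section 3.1).** The text reads "Power analysis indicates that in a single tailed test with an alpha level of .05 and a power of .95" and, for an effect size of 0.40 to 0.45, arrives at "an appropriate n=60 (ten Study subjects per site"). It names no outcome, visit contrast or test. The chart it points to is missing from the supplied text.

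**Outcomes (Section 10).** "The minimum objective data that will be reported is acuity, contrast, reading speed", each without the device at the start and with it at the end. Then: "Further objective data is the comparison between the initial VFQ, and RAND SF-36 scores" and their change by the end of the study. That makes five named outcomes, none ranked above another.

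**Tests (Section 10).** "Repeated measures Analysis of Variance (ANOVA) and t-tests will be used to compare the effect of the eSight devices on all dependent variables" that meet parametric assumptions. Categorical variables and those that fail the assumptions go to "repeated-measures non-parametric techniques (e.g. Friedman Test"). Every quantitative outcome is therefore tested one way or the other.

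**Further outcomes (Section 4.1).** "Step 9.07 Cohn-Kanade Facial Recognition Test" and "Step 9.08 Melbourne Low-Vision ADL Index Test (MLVAI") repeat measures first taken without the device at Steps 3.12 and 3.13.

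**Objectives (Section 2).** Six bullets, none called primary.

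**The concern.** A power of .95 in a single-tailed test describes one comparison. The plan has at least seven outcomes to test and does not say which of them that comparison is. Two things follow.

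- If several outcomes are each tested at .05 and one is significant, a reader cannot tell whether it was the planned result or the best of several. Choosing the main comparison after the data have been seen does not repair this.
- If VFQ-48 or SF-36 shows no change, the stated .95 cannot be used to interpret that result, because nothing attaches the .95 to either.

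Section 1 says that the study should guide patients and physicians on the benefits to expect from a $15,000 device, so it matters which result carries that message. Acuity is the easiest outcome to show: Step 3.09 bases advancement partly on a gain of at least four ETDRS lines with the device.

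**Working it through.** **1. Reproduce the plan's figure.** Inputs from Section 3.1: one-sided α = .05, power .95, effect d = 0.40 to 0.45, n = 60. Assumption, since no test is named: a paired t-test with d = mean change / SD of change.

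Power = P(T > t₀.₉₅,ₙ₋₁), where T is noncentral t with n − 1 degrees of freedom and noncentrality d√n. At n = 60 the critical value is 1.671. At d = 0.40 the noncentrality is 0.40 × √60 = 3.098.

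| d | one-sided n for .95 | one-sided power, n = 60 | two-sided power, n = 60 |
|---|---|---|---|
| 0.40 | 70 | .922 | .862 |
| 0.425 | 62 | .946 | .899 |
| 0.43 | 60 | .950 | .906 |
| 0.45 | 55 | .964 | .929 |

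Sixty lies inside the range 55 to 70 and gives .95 at d of about 0.43. The sample size is consistent with its stated inputs.

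**2. Count the outcomes.** Section 10 names acuity, contrast, reading speed, VFQ and SF-36 (5). Adding facial recognition and MLVAI gives 7. The eSight-8 (Steps 2.03 and 8.02) and goal satisfaction (Steps 3.01 and 9.01) are also repeated but are left out of this count.

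**3. Chance of at least one false positive.** Use one-sided .05 for each test, as in Section 3.1. Leave out acuity, since an outcome selected on at Step 3.09 cannot fairly be treated as unchanged. Assume that no other outcome changes. That leaves k = 4 named outcomes, or k = 6 with facial recognition and MLVAI.

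- Independent: 1 − 0.95ᵏ, so 1 − 0.95⁴ = .185 and 1 − 0.95⁶ = .265.
- Common correlation ρ between normal test statistics: 1 − ∫ φ(u) Φ((1.645 − √ρ·u)/√(1 − ρ))ᵏ du. The documents give no correlations, so ρ is an assumed range.

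| k | independent | ρ = 0.3 | ρ = 0.5 | ρ = 0.7 |
|---|---|---|---|---|
| 4 | 19% | 16% | 14% | 12% |
| 6 | 26% | 22% | 19% | 15% |

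**4. Effect of losses.** Section 3.1 expects low attrition but gives no rate and no inflation, and Section 5 replaces withdrawals only if time permits. With an assumed 10% loss, 60 × 0.9 = 54 are analysed. One-sided power is then .90 at 0.40, .93 at 0.43 and .95 at 0.45.

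**5. Which final score counts.** VFQ-48 has one numbered final step (8.01, telephone), but the introduction to Step 9 also mentions a VFQ-48 in clinic. SF-36 has one numbered final step (9.02), but the introduction to Step 8 also mentions it. Section 10 refers only to the end of the study.

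**The case against.** **The plan already limits selective reporting.** This stands in part. Section 10 commits to reporting acuity, contrast and reading speed, fixes their contrast, and names VFQ and SF-36 change. A reader might infer that any of seven outcomes could be put forward and the rest dropped; the text does not allow that for the first three. What stays open is which result is the main one and how the others are judged. A commitment to report does not control the error rate.

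**The study is exploratory.** Several Section 2 objectives read that way, and the label would be acceptable. The plan does not use it, however: it states a power and seeks conclusions on efficacy.

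**The error rates are hypothetical.** They are, and a larger figure is tempting: all seven outcomes as independent nulls give 1 − 0.95⁷ = 30%. That counts acuity as a null outcome although Step 3.09 selects on it. The smaller figures are used here, and the gap in the plan does not depend on them.

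**The sample size must be wrong or too small.** A reader might infer this. The documents do not support it: 60 is reproduced within the stated range, and one pre-specified comparison needs no split of α.

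**The missing chart may name the outcome.** It may, so the statement about Section 3.1 is confined to its readable text. A chart naming an outcome would still leave Section 10 without a ranking or a multiplicity rule.

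**The questionnaire timing is a drafting mismatch.** Largely so. Each instrument has one numbered final step, and reconciling the introductory sentences settles it.

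**Conclusion.** The point holds as a gap in specification and should be corrected. The supplied text tests at least seven outcomes with no primary comparison and no multiplicity rule, and the readable power statement belongs to none of them.

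Under the stated assumptions (one-sided .05, acuity left out, no true change elsewhere), the chance of at least one false positive is 12 to 19% over four outcomes and 15 to 26% over six, across correlations from 0.7 down to independence. Leaving out acuity alone is a simplification: baseline VFQ-48 answers also feed an advancement decision (Step 2.04).

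No arithmetic error is claimed. For a paired one-sided t-test, the .95 holds from an effect of about 0.43 with 60 analysed, and is .92 at the lower end of the stated range.

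**What to change.** Make these changes before the data are analysed.

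**Section 10.** Suggested wording:

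> The primary comparison is the change in [outcome] from [baseline step] to [final step], by [named paired test] at one-sided .05. All other outcomes are secondary, with Holm adjustment, or are exploratory and labelled so.

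The choice of outcome is the sponsor's, preferably one that does not feed an advancement decision. Acuity (Step 3.09) and VFQ-48 (Step 2.04) both do. If either is chosen, the report should say that selection and possible regression to the mean may contribute to the change.

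**Final scores.** If VFQ-48 or SF-36 is used, its final score is the numbered step (8.01 or 9.02), and the introductory sentences of Steps 8 and 9 are reconciled with this.

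**Section 3.1.** State that the calculation applies to the primary comparison, with the test and effect metric confirmed against the chart. For a paired one-sided t-test, give power with 60 analysed as .92 at 0.40, .95 at about 0.43 and .96 at 0.45, and say that it is lower if withdrawals are not replaced (for example .90 / .93 / .95 with 54 analysed). If a two-sided primary test is chosen, restate power as .86 to .93 with 60 analysed, which is below .95 over the whole range.

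**Cost.** Wording only. The sponsor commits to one comparison and states a less favourable power at the low end of the effect range.

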3.3. Exclusion Criteria

1. Subject must not be currently undergoing any medical or surgical procedures resulting in unstable vision.
2. Subjects for whom their vision, for whatever reason, can be considered unstable.
3. Subjects who have undergone cataract, refractive, or other surgical procedures related to vision in the six month period prior to the study.
4. Subjects who have undergone any eyesight-related injections (e.g. anti-VEGF) in the six month period prior to the study.
5. Subjects unable or unwilling to adhere to the examination schedules as they are described in the study protocol. This may also include Subjects already enrolled who, for whatever reason become unable or unwilling to continue the study. This may also include subjects for whom the travel time to/from the study site is unacceptable.
6. Subjects who self report a history of alcoholism or use of illegal drugs, Subjects who exhibit clinical evidence of depression, poor motivation, emotional or intellectual problems, who are deemed unsuitable psychologically or physiologically for study participation by the investigator.
7. Subjects who may have a conflict of interest with eSight Corp, which could reasonably influence their participation in the study.

4. Study Design

The Quality of Life and Functional Visual Improvement Study Using eSight Wearable Video Eyewear is a prospective multi-site study. The main elements of the study are shown in the flowchart below. Decision points are shown as diamonds. Note that the flowchart below only shows activity for the extended arm (n=60), not the larger screening arm.

As indicated on the chart, the red boxes are activities conducted by eSight. The green and blue boxes are conducted at the study site, by a research assistant, Occupational Therapist, Certified Low Vision Therapist or Eyecare Physician respectively (or supervised and trained designate). Over the course of the study there are four visits by the subject to the study site as indicated by the larger grey boxes. Tests conducted during the first visit are without the eSight device. Subsequent tests deploy the eSight device. Tests within each visit (grey boxes), do not necessarily need to be in the order presented above.

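### Section 10 does not say who is analysed, and its named tests drop anyone without a final value, so the reported gain is overstated if people stop because the device helps them little

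*Combined protocol and SAP*

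**What the plan says.** Section 10 sets the minimum objective report as acuity, contrast and reading speed, measured "without eSight Eyewear at the beginning of the trial, and with eSight Eyewear at its conclusion". It adds "the comparison between the initial VFQ, and RAND SF-36 scores, and the change, if any, in score at the conclusion of the study".

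The methods are brief. "Repeated measures Analysis of Variance (ANOVA) and t-tests will be used to compare the effect of the eSight devices on all dependent variables" that meet parametric assumptions. For the rest, "Categorical variables or those who do not adhere to parametric assumptions will be compared using repeated-measures non-parametric techniques (e.g. Friedman Test"). The software is SPSS 22.

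Section 4.1 has acuity, contrast, MNREAD, facial recognition and the MLVAI tested at Step 3 without the device, at Step 4 with it, and again at Step 9, where the repeats are "intended to assess changes in visual function and functional visual performance over time using eSight Eyewear".

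Section 5 allows a subject to leave by choice, for a device-related effect, for illness or for non-compliance. It then says: "Time permitting, subjects that withdraw from the study will be replaced by other candidates". Section 3.1 expects attrition to be low but gives no figure.

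No section defines an analysis set, a rule for missing values or a sensitivity analysis. None says how withdrawn subjects and their replacements enter the results.

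**The concern.** A paired t-test needs both values. A classical repeated-measures ANOVA or a Friedman test needs every value compared. With no other rule stated, a subject who is fitted at Step 4 and has no final value disappears from the start-to-conclusion comparison. A replacement restores the count but does not stand in for the person who left.

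There is no control group, so nothing else in the design would show the effect of this selection. Some of the reasons for leaving listed in Section 5 could plausibly go with low benefit. Section 2 also sets out to characterise people whom the device helps little or not at all, and those are the subjects a completer analysis would tend to lose. A reader of the planned result could not tell whether it describes everyone fitted or only those who stayed.

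**Working it through.** **The plan's own figure.** Section 3.1 gives a one-sided alpha of .05, power .95 and an effect size of 0.40 to 0.45. The normal approximation for a paired comparison is n = ((1.645 + 1.645)/d)², which gives 68 at d = 0.40 and 54 at d = 0.45. The exact t calculation gives 70 and 55, and 60 at d = 0.43. So n = 60 is reproduced inside the stated range, as a number of complete pairs. It carries no allowance for loss: 60 completers need 60/0.95 = 64, 60/0.90 = 67 or 60/0.80 = 75 fitted at 5, 10 or 20% loss (rounded up).

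**Completer overstatement.** Let w be the share who stop and r the stoppers' mean gain divided by the completers'. Both are assumptions. With 60 fitted, w = 5, 10 or 20% is 3, 6 or 12 people. The mean gain in everyone fitted is the completers' gain times (1 − w) + wr, so

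overstatement = 1/((1 − w) + wr) − 1.

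| Stoppers' gain relative to completers | w = 5% | w = 10% | w = 20% |
|---|---|---|---|
| r = 1 (stopping unrelated to benefit) | 0% | 0% | 0% |
| r = 0.5 | 1/0.975 − 1 = 2.6% | 1/0.95 − 1 = 5.3% | 1/0.90 − 1 = 11.1% |
| r = 0 | 1/0.95 − 1 = 5.3% | 1/0.90 − 1 = 11.1% | 1/0.80 − 1 = 25.0% |

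**If stoppers worsen.** The r = 0 row is not a ceiling. Take a true mean change of 0.425 SD, a normal latent tendency to stay that correlates 0.5 with the change, and loss of the lowest share w. The completer mean is 0.425 + 0.5·φ(z_w)/(1 − w), which is 0.479, 0.522 and 0.600. Dividing by 0.425 gives overstatement of about 13, 23 and 41%. The stoppers' own mean change in this model is negative.

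**Setting missing changes to zero.** The relative error is (1 − w)/((1 − w) + wr) − 1. At r = 1 it is −5, −10 and −20%. At r = 0.5 it is −2.6, −5.3 and −11.1%. At r = 0 it is nil. In the worsening model above it is 0.95 × 0.479/0.425 − 1 = +7%, 0.90 × 0.522/0.425 − 1 = +11% and 0.80 × 0.600/0.425 − 1 = +13%. The zero-change result is therefore conservative only if stoppers do not worsen on average.

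**What a mixed model recovers.** Let ρ be the correlation between the gains at Step 4 and Step 9. If stopping depends on the gain already seen at Step 4, a likelihood model on all visits removes the bias. In simulation (60 fitted, 6,000 runs, mean gain 0.43 SD, ρ = 0.5, r = 0.5) its error was −0.4, 0.0 and −0.5%, against +2.2, +5.3 and +10.8% for completers. If stopping depends on the unseen Step 9 gain, about 1 − ρ² of the bias remains. At ρ = 0.5 that is 0.75 × 2.6, 5.3 and 11.1, or about 2, 4 and 8%. The simulated values were +2.5, +3.6 and +8.6%, with Monte Carlo error of about 0.4 points.

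**Replacement.** Under the same latent model with no true mean change and correlation 0.5, a one-sided 5% test on completers rejects in 10.6, 18.0 and 34.9% of 20,000 simulated trials at 5, 10 and 20% loss. Replacing leavers until there are 60 completers gives 11.0, 19.5 and 40.7%. With correlation 0 the rate stays near 5%. Replacement restores the number analysed, not who they represent.

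**The case against.** The strongest reply is that every size above is assumed. Loss may be small after the screening at Step 3.09, and at 5% loss with half the gain the overstatement is under 3%. Step 3.09 weighs a minimum 4-line ETDRS improvement (4 × 5 letters × 0.02 = 0.40 log units), so a zero gain is implausible for acuity. Section 5 also says "Every effort will be made to have withdrawn subjects complete the follow-up procedures (Part 4"), and Section 11.1 has each withdrawal reported to the IRB. All of this stands as a limit on size. None of it says who is analysed, or whether data from withdrawn subjects are used.

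A reader might also infer more than the document supports:

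- **That Exclusion 5 removes fitted subjects or their data.** It says "This may also include Subjects already enrolled who, for whatever reason become unable or unwilling to continue the study". Section 3.1 uses enrolment for the screening arm, so this may concern people never fitted. No text says collected data are discarded.
- **That the Part 4 reference leads nowhere.** The flowchart with the four site visits is not reproduced in the text reviewed and may carry that label.
- **That stoppers are also lost from Step 3 versus Step 4.** Section 10 never specifies a three-visit ANOVA, and a paired t-test on those two steps would keep them.
- **That the telephone survey protects SF-36.** The Step 8 introduction names SF-36, but its listed items do not. SF-36 is repeated in clinic at Step 9.02.

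**Conclusion.** The point holds in a conditional form. The named tests and the absence of any analysis set make the start-to-conclusion change a completer estimate. It is unbiased if stopping is unrelated to benefit and too large if people stop because they gain little: about 3, 5 or 11% at 5, 10 or 20% loss with half the gain, 5, 11 or 25% with none, and more if stoppers worsen. The loss rates and relative gains are assumptions, because the document gives neither. The 25% figure should not be read as an upper limit, and the document does not show that the result will be biased. This should be corrected before analysis. It is more than missing detail, because five outcomes are tested at three visits and a method that uses those data is available in the named software.

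**What to change.** In Section 10:

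1. Define the analysis set as all subjects fitted with the device at Step 4. Replacements are added to those who withdraw and not substituted for them. Align the replacement sentence in Section 5.
2. For continuous outcomes tested at Steps 3, 4 and 9, replace repeated-measures ANOVA with a linear mixed model on all available visits (SPSS MIXED). State its missing-at-random assumption, and that it corrects only partly if stopping depends on final benefit that was never observed.
3. If Step 3 is compared with Step 4 by a rank method, use everyone who has both values.
4. VFQ-48 and SF-36 are planned only at the start and the end, so the extra Step 4 visit cannot help. Add a sensitivity analysis that sets the change to zero for subjects without a final value. Describe it as one scenario that is conservative only if stoppers do not worsen on average, not as a bound.
5. Report the number who stop, with reasons.

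The cost is a few sentences and slightly more analysis in the same package. The estimate may come out somewhat smaller.
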